7.1.7.5 Hugo™ RAS Large Needle Driver

The Hugo™ RAS Large Needle Driver is a Hugo™ RAS wristed instrument with an end effector designed to hold and drive large needles.

7.1.7.6 Hugo™ RAS Extra Large Needle Driver

The Hugo™ RAS Extra Large Needle Driver is a Hugo™ RAS wristed instrument with an end effector designed to hold and drive large needles.

7.1.7.7 Hugo™ RAS Cadiere Forceps

The Hugo™ RAS Cadiere Forceps is a Hugo™ RAS wristed instrument with a rounded, wide fenestrated jaw end effector for tissue manipulation including grasping, blunt dissection, approximation, and suturing.

7.1.7.8 Hugo™ RAS Double Fenestrated Grasper

The Hugo™ RAS Double Fenestrated Grasper is a Hugo™ RAS wristed instrument with a long fenestrated jaw end effector for tissue manipulation including grasping, blunt dissection, approximation, and suturing.

7.1.7.9 Hugo™ RAS Toothed Grasper

The Hugo™ RAS Toothed Grasper is a Hugo™ RAS wristed instrument with a toothed claw grasper end effector for tissue manipulation including grasping and approximation.

7.18 Software

Software versions will be captured in shipment records, including the clinical shipment/return form.

7.2 Manufacturer

Please see Table 3 and Table 4.

7.3 Packaging

The Medtronic Hugo™ RAS System components and instruments will be labelled as investigational according to regulations, such as: "CAUTION – Investigational device. Limited by Federal (or United States) law to investigational use".

7.4 Intended Population

The target population will consist of subjects 22 years of age or older indicated for a urological robotic assisted surgery with Hugo™ RAS.

7.5 Equipment

The necessary equipment to complete the study procedure, includes but is not limited to, the lists below.

Medtronic Hugo™ RAS System (Investigational Device):

The investigational device will be provided by the study sponsor (Table 3).

Table 3. Investigational Device

SKU	Description (Branding Company)	Investigational or Commercially Available
MRASC0001	Surgeon Console (Medtronic)	Investigational
MRASC0002	Arm Cart Assembly (Medtronic)	Investigational
MRASC0003	Tower, 120v (Medtronic)	Investigational
MRASA0002	Endoscope Adapter (Covidien)	Investigational
MRASA0003	Sterile Interface Module (Covidien)	Investigational
MRASA0004	3D Glasses, Surgeon Only (Medtronic)	Investigational
MRASA0005	3D Glasses, Observer (Medtronic)	Investigational
MRASA0006	Assy, Sterile Pouch, Robotic Arm Drape (Covidien)	Investigational
MRASA0007	Assy, Sterile Pouch, Robotic Upper Cart Drape (Covidien)	Investigational
MRASA0008	Assy, Sterile Pouch, Robotic Lower Cart Drape (Covidien)	Investigational
MRASA0009	Sterile Monopolar Cover (Covidien)	Investigational
MRASI0001	Monopolar Curved Shears (Covidien)	Investigational
MRASI0004	Bipolar Fenestrated Grasper (Covidien)	Investigational
MRASI0005	Bipolar Maryland Forceps (Covidien)	Investigational
MRASI0006	Large Needle Driver (Covidien)	Investigational
MRASI0007	Extra Large Needle Driver (Covidien)	Investigational

Medtronic Business Restricted

This document is electronically controlled

CONFIDENTIAL 056-F275 Rev E Clinical Investigation Plan Template

Medtronic Expand URO Clinical Investigation Plan

MDT19051EINURO

Version 9.0

Page 31 of 111

Medtronic

SKU	Description (Branding Company)	Investigational or Commercially Available
MRASI0011	Cadiere Forceps (Covidien)	Investigational
MRASI0012	Double Fenestrated Grasper (Covidien)	Investigational
MRASI0016	Toothed Grasper (Covidien)	Investigational

NOTE: All Hugo™ RAS SKUs regardless of branding are manufactured by Covidien LP, [name].

Medtronic Hugo™ RAS System-Compatible Components:

The following components are required, if applicable, for study procedures and will be provided by the study sponsor.

Table 4. Medtronic Hugo™ RAS System-Compatible Components

SKU	Product Description (Manufacturer)	Investigational or Commercially Available
TC200US	Storz 3D Camera Control / System (Karl Storz)	Commercially Available
TC302US	Storz 3D SCB Interface & Spies System (Karl Storz)	Commercially Available
TL 300	Storz Cold Light Fountain Power LED 300 (Karl Storz)	Commercially Available
26605BA	Storz 30 Degree 3D Endoscope (Karl Storz)	Commercially Available
26605AA	Storz 0 Degree 3D Endoscope (Karl Storz)	Commercially Available
495VIT	Storz Fiber Optic Light 5.5m Cable (Karl Storz)	Commercially Available
TC015	Storz Video Extension Cable (Karl Storz)	Commercially Available
VLFT10GEN	FT-10 Generator (Covidien)	Commercially Available
FT0510	Reusable Monopolar Electrosurgery Cord (Covidien)	Commercially Available

Medtronic Business Restricted

This document is electronically controlled

CONFIDENTIAL 056-F275 Rev E Clinical Investigation Plan Template

Medtronic Expand URO Clinical Investigation Plan

MDT19051EINURO

Version 9.0

Page 32 of 111

Medtronic

SKU	Product Description (Manufacturer)	Investigational or Commercially Available
E0020V	Reusable Bipolar Electrosurgery Cord (Covidien)	Commercially Available
RNONB8STF	VersaOne™ Bladeless Positioning Trocar System – 8mm standard fixation trocar (Covidien)	Commercially Available
RONB11STF	VersaOne™ Optical Positioning Trocar System – 11mm standard fixation trocar (Covidien)	Commercially Available
RSEAL	VersaOne™ Reusable Positioning Trocar System – 5mm - 12mm Seal (Covidien)	Commercially Available
ONB5STF	5MM Auxiliary Port, Versaone OPT 5 MM STD Trocar	Commercially Available
OBTNONB8ST	VersaOne™ Reusable Positioning Trocar System – 8mm standard Bladeless Obturator (Covidien)	Commercially Available
OBTONB11ST	VersaOne™ Reusable Positioning Trocar System – 11mm standard Optical Obturator (Covidien)	Commercially Available
ONB12STF	12MM Auxiliary Port, Versaone OPT 12 MM STD Trocar	Commercially Available
RC8STS	VersaOne™ Reusable Positioning Trocar System – 8mm standard Reusable Positioning Cannula (Covidien)	Commercially Available
RC11STS	VersaOne™ Reusable Positioning Trocar System – 11 mm standard Reusable Positioning Cannula (Covidien)	Commercially Available
KSZ-39301TS	Endoscope Sterilization Tray	Commercially Available

Medtronic Business Restricted

This document is electronically controlled

CONFIDENTIAL 056-F275 Rev E Clinical Investigation Plan Template

Other Equipment:

The following components may be required for the study procedures and will not be provided by the study sponsor.

- Energy Sealing Device
- Linear Stapler
- Reticulating Stapler
- Surgical Clips

7.6 Product Use

This information is contained in the IFU ([Appendix 18.3](#)). The IFU accompanying the device should always be consulted.

The device will be in contact with the urologic region including tissues and body fluids. All device components and materials are biocompatible. Device biocompatibility testing and results are summarized in the Report of Prior Investigations ([Appendix 18.2](#)).

For instructions on study product scope of use and handling, please refer to the IFU ([Appendix 18.3](#)).

7.7 Product Training Materials

See [Table 5](#). The Medtronic Hugo™ RAS System should only be used by surgeons and OR staff who have received specific product training provided by Medtronic in the use of this device. The training provided by Medtronic does not replace the necessary medical training and experience required to perform surgery.

Surgeons and hospital staff performing study procedures will be required to demonstrate a minimum level of professional competency and product training outlined below prior to performing study procedures.

Technical Training focus areas include:

- Hugo™ System Operation
- Hugo™ System Surgical Field Set-up
- Hugo™ System Console Skills
- Hugo™ System Clinical Application
- RAS Fundamental Surgical Task Skills

Table 5. Professional Competency and Product Training

	Professional Competency	Product Training
Principal Investigator(s)	
At least 2 years of surgical training and/or experience conducting laparoscopic surgeryAt least 2 years robotic experience with the specific study procedure(s) they will be performing for the studyOn average, completing 10-12 procedures annually (specifically the study procedure (s) they will be performing for the study)	
Completed simulator exercises on the Medtronic Hugo™ RAS SystemDidactic training on the capability and features of the Medtronic Hugo™ RAS SystemCompleted hands-on training course
OR Staff	
At least 2 years of surgical training and/or experience in robotic surgery	
Didactic training on the capability and features of the Medtronic Hugo™ RAS SystemCompleted hands-on training course

All study site personnel will be trained on relevant information prior to their participation in the study.

7.8 Product Receipt and Tracking

The Medtronic Hugo™ RAS System and necessary equipment will be shipped to each site and tracked. In the case that model, lot, and/or serial numbers are not available on the packaging, the sponsor will assign lot, batch, or serial numbers to the study product in order to maintain traceability. Each site will review the content of the shipping form and investigational product upon receipt.

The use of the device for a procedure or disposition of the devices (e.g., if returned due to damage upon arrival) will be recorded on a site device accountability log to be maintained at the site and reconciled by the end of the study.

The Medtronic Hugo™ RAS System and necessary instruments will be provided to each site upon sponsor collection and approval of all required regulatory documents.

The date when the site receives the Hugo™ RAS System, will be recorded and maintained during the clinical investigation. Each Medtronic Device and Device Instrument will be traced with the serial or lot number.

7.9 Product Storage

Access to the study should be limited to designated study staff only. Study device components should be covered with sponsor provided device covers when not in use for study procedures.

Study devices should be kept in or otherwise contained where only qualified study personnel can access the device (i.e., locked or secured). This area/container should be kept at ambient temperatures without exposure to water with adequate provisions for maintaining ambient temperatures if a loss of power is experienced. If the devices are exposed to water or a drastic change in temperature, sites should contact the study team for possible replacement devices.

7.10 Product Return

It is the responsibility of the site to return the Medtronic Hugo™ RAS System to Medtronic at the end of the study, along with any unused or expired Medtronic Hugo™ RAS wristed instruments or other components. Sites should follow instructions and complete all appropriate forms provided by the study team for product return.

7.11 Product Accountability

Access should be limited to designated study staff only. A device accountability log will be maintained at the site and reconciled by the end of the study. It is the site's responsibility to document the receipt (which includes shipping/dispersal date, the quantity, model, lot, and serial numbers, and expiration date), disposition of the product (per subject use, including amount used, amount remaining, etc.), transfer (if applicable), and return of all unopened investigational medical devices at the end of the study. The sponsor shall also keep records to document the physical location of all investigational devices from shipment of investigational devices to the investigation sites until return or disposal.

Medtronic will perform periodic reconciliation of the investigational product to ensure traceability through monitoring.

8. Study Site Requirements

8.1 Investigator/Investigation Site Selection

All Investigators managing the subject's urologic condition must be qualified practitioners and experienced in the diagnosis and treatment of subjects with study specific urologic conditions. All physicians must be experienced and/or trained in the handling of the Medtronic Hugo™ RAS System.

The role of the Principal Investigator is to implement and manage the day-to-day conduct of the clinical investigation as well as ensure data integrity and the rights, safety and well-being of the subjects involved in the clinical investigation.

The Principal Investigator shall:

- Be qualified by education, training, and experience to assume responsibility for the proper conduct of the clinical investigation
- Be experienced in the field of application and training in the use of Medtronic Hugo™ RAS

Medtronic Business Restricted

This document is electronically controlled

CONFIDENTIAL 056-F275 Rev E Clinical Investigation Plan Template

System.

- Disclose potential conflicts of interest, including financial, that interfere with the conduct of the clinical investigation or interpretation of results
- Be able to demonstrate that the proposed investigational study site:
 - Has the required number of eligible subjects needed within the recruitment period
 - Has one or more qualified Investigators, a qualified investigational study site team and adequate facilities for the foreseen duration of the clinical investigation

Study site personnel training will be completed and documented prior to participation in this study.

8.2 Study Site Activation

During the activation process (prior to subject enrollment), Medtronic will train study site personnel on the clinical investigation plan, on relevant standards and regulations, informed consent, and on data collection and reporting tools. If new members join the study site team, they will receive training on the applicable study requirements relevant to their role before contributing to the study.

Prior to performing study related activities, all regulatory requirements shall be fulfilled, including, but not limited to the following:

- Institutional review board (IRB) approval (and voting list, as required by local law) of the current version of the clinical investigation plan (CIP) and informed consent (IC)
- Regulatory authority (RA) approval or notification (as required per local law)
- Fully executed clinical trial agreement (CTA)
- Financial disclosure (if applicable)
- Curriculum vitae (CV) of Investigators and key members of the investigation study site team (as required). The signature on the CV must be dated within 3 years prior to the date of activation of the study site.
- Documentation of delegated tasks
- Documentation of study training
- Additional requirements imposed by local regulations, the IRB and RA shall be followed, if appropriate

In addition, all participating study site staff must be trained on the current version of the CIP as well as on the applicable study requirements depending on their role and must be delegated by the Principal Investigator to perform study related activities.

Medtronic will provide each study site with documentation of study site/Investigator readiness; this letter must be received prior to performing study related activities.

8.3 Role of the Sponsor Representatives

Sponsor representatives may provide support at the study site as required for the study under supervision of the Principal Investigator, including:

- Provide study training relevant and pertinent to the involvement of personnel conducting study activities and Investigator responsibilities
- Technical support will be provided during the procedure under the supervision of a study Investigator, but no data entry, shall be performed by Medtronic personnel or their representatives at study sites
- Monitoring and auditing activities

In addition, for this study, sponsor representatives may be authorized by the Principal Investigator to perform the following significant trial related duties:

- Support study Investigators in performing the study procedure
- Support data collection during the procedure and device testing
- Support data collection during the study follow-up visits. Any data collection completed by Medtronic personnel will be clearly identified as such.

9. Selection of Subjects

9.1 Study Population

A minimum of 141 subjects will be enrolled at up to 6 sites in the USA.

The Medtronic Hugo™ RAS System is intended to be used in this study for urologic surgical procedures including radical prostatectomy, radical cystectomy, nephrectomy (partial or radical) procedures to be performed in subjects that meet the inclusion criteria listed in **Section 9.3**.

Subject conditions and/or diagnoses may include, but are not limited to, prostate cancer, pelvic tumors, interstitial cystitis, congenital abnormalities, end-stage kidney disease (kidney failure), renal tumor, kidney injury.

The subjects must be acceptable candidates for a fully robotic assisted procedure with the Medtronic Hugo™ RAS System, as determined by the investigating surgeon.

9.2 Subject Enrollment

A subject is considered enrolled in the study when the consent process is signed and dated. Screening data will not be collected for the study until the subject has been determined to be eligible for the study and signed consent (see **Section 10.2** for details). If the subject is consented prior to the day of surgery, a re-verification of eligibility will be signed off by the PI or Sub-I on the day of surgery. As soon as the surgical procedure has begun with the Medtronic Hugo™ RAS System, the subject must be followed

Medtronic Business Restricted

This document is electronically controlled

CONFIDENTIAL 056-F275 Rev E Clinical Investigation Plan Template

regardless of whether or not the subject completed the surgical procedure with the Medtronic Hugo™ RAS System. Subject enrollment will be consecutive at the institution according to required procedure types and eligibility criteria. See **Section 9.3** for additional details.

9.3 Inclusion Criteria

1. Adult subjects (age \geq 22 years) as required by local law
2. Subject has been indicated for a radical prostatectomy, radical cystectomy, or nephrectomy (partial or radical) surgical procedure
3. Subject is an acceptable candidate for a fully robotic assisted surgical procedure, a laparoscopic surgical procedure or an open surgical procedure
4. The subject is willing to participate and consents to participate, as documented by signed informed consent form

9.4 Exclusion Criteria

1. Subjects for which minimally invasive surgery is contraindicated as determined by the Investigator
2. Subjects with comorbidities or medical characteristics, which would preclude the surgical procedure in the opinion of the Investigator
3. The patient has been diagnosed with a bleeding disorder and/or cannot be removed from their anticoagulants prior to surgery based on surgeon discretion and standard-of-care
4. Non-oncology subjects with an estimated life expectancy of less than 6 months; oncology subjects considered for cystectomy with a life expectancy less than 24 months; oncology subjects considered for nephrectomy with a life expectancy less than 60 months; oncology subjects considered for prostatectomy with less than a 10-year life expectancy.
5. Female subjects pregnant at the time of the surgical procedure
6. Subjects who are considered to be part of a vulnerable population (e.g., prisoners or those without sufficient mental capacity)
7. Subjects who have participated in an investigational drug or device research study within thirty (30) days of enrollment that would interfere with this study
8. Subjects with active infections including but not limited to pneumonia, urinary tract, cellulitis, or bacteremia

10. Study Procedures

10.1 Schedule of Events

10.1.1 Screening Visit (Visit 1)

A screening visit will be performed within 30 days prior to the scheduled procedure and may be

Medtronic Business Restricted

This document is electronically controlled

CONFIDENTIAL 056-F275 Rev E Clinical Investigation Plan Template

combined with the surgical procedure visit. Subjects will be consented before any procedures specific to the study are undertaken. If the subject is consented prior to the day of surgery, a re-verification of eligibility will be signed off by the PI or Sub-I on the day of surgery. The purpose and all aspects of the study will be explained to the subject. Subjects who agree to study participation must sign and personally date an IRB-approved informed consent form prior to participating in any study activities.

Once informed consent has been obtained according to IRB requirements and eligibility is confirmed, the subject's demographics and medical history will be assessed. Relevant medical and surgical history will be assessed and included in the electronic case report form (eCRF).

10.1.2 Surgical Procedure Visit (Visit 2)

The subject will arrive for admission to the hospital, will be checked in, placed in pre-op, and prepped for surgery according to local standard practices. Upon arrival to the operating room the subject will be placed on the plinth, the anesthesia and surgical teams will place the subject in position and the operation will begin at the time of the first incision. The study Investigator should perform the surgical procedure according to the appropriate standard of procedures, practices, and set-up guidelines. See **Table 6** for the data that will be collected during this procedure.

10.1.3 Up to Hospital Discharge (Visit 2.1)

Visit 2.1 will begin when the subject arrives in recovery after the operation is over and will last through the subject being discharged from the hospital. All standard-of-care practices will be followed for this visit. See **Table 6** for the data that will be collected during this procedure.

10.1.4 Post-Operative Follow-Up Visit (Visit 3)

The 30 (+7) days post-operative visit should be made by an in-person follow-up visit to the site.

Only in extreme circumstances (i.e., COVID-related in person restrictions at the site, difficulties of the subject travelling to the site), the 30 (+7) day follow-up visit may be conducted via phone call and/or video conference for the collection of adverse event and medical follow-up information.

10.1.5 Post-Operative Follow-Up Visits (Visit 4-8)

Post-operative visits 4-8 for oncologic subjects will be made via a phone call to assess overall survival, progression-free survival, and disease-free survival.

Medtronic Expand URO Clinical Investigation Plan

MDT19051EINURO

Version 9.0

Page 40 of 111

Medtronic

Table 6. Data Collection and Study Procedure Requirements at Subject Visits

Procedure/Assessment	Screening (Day -30 to 0) Visit 1	Surgical Procedure (Day 0) Visit 2	Hospital Discharge Visit 2.1	Follow-Up (30+7 Days) Visit 3	Follow-up (Years 1 - 5) (+/- 3 mo. window) Visits 4-8
	May be Combined				
Informed Consent Form ¹	X	X			
Eligibility Criteria	X	X			
Demographic Data	X				
Medical/Surgical History	X				
Concomitant Medication(s)	X	X	X	X	
Lab Values (if applicable)	X	X	X	X	
Robot Setup Time		X			
Total Operative Time (skin to skin)		X			
Surgeon Console Time		X			
Instruments Used		X			
Estimated Blood Loss		X			
Transfusion ³		X	X	X	
Conversion to a robotic-assisted approach utilizing an FDA cleared robotic-assisted device, open or manual laparoscopy		X			
Robot Take Down Time		X			
Warm Ischemia Time (if applicable)		X			
Anastomotic Leak Test performed (if applicable)		X			
Anastomotic Stricture (if applicable)		X			
Rate of Positive Circumferential Margins on Final Pathology (if applicable)		X			
Margin (mm) (if applicable)			X		

Medtronic Business Restricted

This document is electronically controlled

CONFIDENTIAL 056-F275 Rev E Clinical Investigation Plan Template

Medtronic Expand URO Clinical Investigation Plan

MDT19051EINURO

Version 9.0

Page 41 of 111

Medtronic

Procedure/Assessment	Screening (Day -30 to 0) Visit 1	Surgical Procedure (Day 0) Visit 2	Hospital Discharge Visit 2.1	Follow-Up (30+7 Days) Visit 3	Follow-up (Years 1 - 5) (+/- 3 mo. window) Visits 4-8
Tumor Size (if applicable)			X		
Tumor Stage (if applicable)			X		
Total number of lymph nodes retrieved			X		
Catheterization Time			X	X	
Mortality			X	X	X
Length of Hospital Stay			X		
Reoperation			X	X	X
Pain Medication			X	X	
Medications if associated with an AE	X	X	X	X	X
Adverse Events ²	X	X	X	X	X
Readmission				X	X
Device Accountability		X			
Device Deficiency		X			
Protocol Deviation Collection (if applicable)	X	X	X	X	X
Study Exit				X	X

¹Study specific procedures may only be performed after subject has agreed to participate and signed the informed consent form.

Screening and informed consent are considered as a process that may occur over multiple days within 30 days prior to procedure. Any new information about the subject's eligibility and willingness to participate must be considered prior to the procedure with the investigational device.

²AEs/SAEs must be followed until resolution or study exit whichever comes first. Adverse Events will be collected from the moment of consent. If any events are ongoing at study exit, they will be monitored by the physician per their institutional standard-of-care.

³Transfusion will be only collected when associated with an adverse event.

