4. Non-oncology subjects with an estimated life expectancy of less than 6 months; oncology subjects considered for cystectomy with a life expectancy less than 24 months; oncology subjects considered for nephrectomy with a life expectancy less than 60 months; oncology subjects considered for prostatectomy with less than a 10-year life expectancy.
5. Female subjects pregnant at the time of the surgical procedure.
6. Subjects who are considered to be part of a vulnerable population (e.g., prisoners or those without sufficient mental capacity)
7. Subjects who have participated in an investigational drug or device research study within thirty (30) days of enrollment that would interfere with this study
8. Subjects with active infections including but not limited to pneumonia, urinary tract, cellulitis, or bacteremia

Medtronic Expand URO Clinical Investigation Plan

MDT19051EINURO

Version 9.0

Page 15 of 111

Medtronic

Study Procedures and Assessments	
Screening, Surgical Procedure, Hospital Discharge, and Post-Discharge Follow-Up (see full protocol for data collection/assessment windows):
 
Screening: To determine study eligibility and collect baseline information (demographics, medications, medical history, surgical history, kidney function).
 
Surgical Procedure: To re-confirm eligibility criteria, procedure set-up and take-down, medications associated with adverse events, intraoperative complication evaluation, disease state evaluation, procedure success, conversion rates, protocol deviation, device deficiency and adverse event evaluation.
 
Up to Hospital Discharge: Adverse event evaluation, subject complication rate, disease state evaluation, protocol deviation and medications associated with adverse events.
 
Post-Discharge Follow-Up: Adverse event evaluation, subject complication rate, disease state evaluation, length of hospital stay, readmission (if applicable), reoperation (if applicable), recurrence (if applicable), protocol deviation, medications associated with adverse events and study exit.

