8	Reoperation Rate	Reoperation through 30 days is identified in a subject if they experience a related (device, procedure, or underlying condition/disease) adverse event that resulted in treatment with a surgical procedure and the AE start date was prior to or during the 30-calendar days post-procedure.
9	Mortality Rate	Death through 30 days is identified as an AE that led to death which occurs during the procedure or up to the 30 calendar-days post-procedure.
10	Device Deficiencies	A subject is identified as experiencing a device deficiency if a device deficiency occurred before, during, or after the subject's procedure.
11	Overall Survival	Subject death will be identified as an adverse event that leads to death where the adverse event start date is on or after the procedure date or if the subject is noted by the site to have died during follow-up. Time to death will be calculated as the difference in days between death and the procedure date.
12	Progression-free Survival	Disease progression will be identified in a subject if their disease state is noted by the site, during follow-up, as "disease reoccurrence, disease progression", or if subject death had been noted. This is assessed as either at the time of the follow-up visit or at the time of last contact, whichever is earlier will be denoted as the time of disease

		progression. Time to disease progression is calculated as the difference in days between disease regression and the procedure date.
13	Disease-free Survival	Disease reoccurrence will be identified in a subject if the subject disease state is noted by the site, during follow-up, as “disease reoccurrence, disease progression”, “disease reoccurrence, disease stable”, or if subject death had been noted. This is assessed either at the time of a follow-up visit or at the time of last contact, whichever is earlier will be denoted as the time of disease reoccurrence. Time to disease reoccurrence will be calculated as the difference in days between disease reoccurrence date and the procedure date.

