7.9.3.5 Analysis Methods

Secondary objectives 1, 4, 5, 7, 8, 9 and 10 will be summarized by surgery as the count and proportion of subjects experiencing the given endpoint, with a 95% confidence interval.

Secondary objectives 2, 3 and 6 will be summarized by surgery performed using mean, standard deviations (SD), median, IQR, and range. A 95% confidence interval will also be calculated.

Secondary objectives 11, 12 and 13 will be evaluated through separate Kaplan-Meier analyses by surgery.² The event for each Kaplan-Meier will be their respective objective endpoint. Subjects will be censored upon study completion (5-year follow-up visit) or they are lost to follow-up without event. For subjects that are lost to follow-up, their last visit date or date of last subject contact will be used as their censor date, whichever occurred later. The 5-year survival will be estimated from the Kaplan-Meier model and a 95% confidence interval will be calculated.

Secondary objective 1 will have three additional exploratory analyses wherein the overall complication rate within 30 days will be limited to each of: related to device, related to procedure, and related to underlying condition. Relatedness in this exploratory analysis will be any rating other than “Not Related” or equivalent.

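### PFS and DFS rest on yearly phone calls with no disease-state row in Table 6 and no stated source evidence, so a recurrence unknown to the site counts as event-free time

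*Protocol*

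**What the plan says.** - **Mode of follow-up.** Protocol 10.1.5: "Post-operative visits 4-8 for oncologic subjects will be made via a phone call to assess overall survival, progression-free survival, and disease-free survival". The matching Table 6 column is headed "Follow-up (Years 1 - 5) (+/- 3 mo. window) Visits 4-8".
- **What Table 6 collects at those visits.** Seven rows are marked: mortality, reoperation, AE-associated medication, adverse events, readmission, protocol deviations and study exit. The laboratory row is marked for Visits 1, 2, 2.1 and 3 only. No row at any visit collects disease state, recurrence, imaging or a tumor marker.
- **What the synopsis lists.** Under Study Procedures and Assessments: "Post-Discharge Follow-Up: Adverse event evaluation, subject complication rate, disease state evaluation, length of hospital stay". The same list goes on to include recurrence where applicable.
- **How the SAP defines the event.** SAP 7.9.3.1, endpoint 12: "Disease progression will be identified in a subject if their disease state is noted by the site, during follow-up", with death also counting. Endpoint 13 (DFS) is built the same way. The event is dated at the follow-up visit or the last contact, whichever is earlier.
- **How the SAP censors.** SAP 7.9.3.5 censors event-free subjects at the 5-year visit. For subjects lost to follow-up, "their last visit date or date of last subject contact will be used as their censor date, whichever occurred later".
- **Role of the endpoints.** They are descriptive with no hypothesis test (SAP 7.9.3.2). The 5-year goals for both PFS and DFS are 15% for nephrectomy, 15% for prostatectomy and 10% for cystectomy (Protocol 14.5).

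**The concern.** PFS and DFS depend on knowing whether disease has returned. The table that controls data collection omits the variable from which the SAP computes them, and neither document says whether the site-noted state rests on a test result, a chart review or what the subject says on the phone. Neither censoring rule asks whether disease was assessed at all. A subject who answers five yearly calls with no disease assessment since surgery can be carried as progression-free and disease-free to year 5.

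Protocol 10.9.6 makes such a subject foreseeable: it lets subjects disengage while telephone follow-up remains acceptable, and data collection requirements then no longer apply.

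The error has one direction, because a missed recurrence can only raise the estimate. The study is single-arm, so no concurrent control shares the under-ascertainment.

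**Working it through.** The plan states no figure on this point, so there is none to reproduce. The check asks which way a missed recurrence moves the estimate, and by how much under stated assumptions.

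**Inputs.** Five-year OS (O) comes from the literature means in Protocol 14.5: 95.4% prostatectomy, 93.1% nephrectomy, 64.5% cystectomy. True 5-year PFS (S) and the share of recurrences detected (q) are not in the documents. They are assumed: S = 80%, 70%, 50% and q = 90%, 70%, 50%.

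**Formula.** Take all deaths as known, visits as exactly yearly and no losses. Nobody is then censored before year 5, and the Kaplan-Meier value at 5 years is the share with no recorded event. These are subjects alive without recurrence (S) plus those alive with a missed recurrence, (1 − q)(O − S). So:

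bias = (1 − q)(O − S)

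A simulation (60,000 subjects per scenario, independent exponential recurrence and death, detection dated at the next yearly visit) was run with exact yearly visits and with a uniform ±3-month window. Bias in percentage points for q = 90% / 70% / 50%:

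| True PFS, OS | O − S | Formula | Simulated, exact visits | Simulated, ±3 months |
|---|---|---|---|---|
| 80%, 95.4% | 15.4 | 1.54 / 4.62 / 7.70 | 1.5 / 4.6 / 7.8 | 2.5 / 5.4 / 8.3 |
| 70%, 93.1% | 23.1 | 2.31 / 6.93 / 11.55 | 2.3 / 6.7 / 11.4 | 3.6 / 8.0 / 12.2 |
| 50%, 64.5% | 14.5 | 1.45 / 4.35 / 7.25 | 1.4 / 4.5 / 7.2 | 2.4 / 5.2 / 8.0 |

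Formula and simulation agree within 0.3 points.

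**Dating.** With q = 100% the simulated bias is 0 for exact visits and about 1 to 1.6 points with the window, because some year-5 detections are dated after 5.0 years. Dating by visit therefore adds a small upward shift of its own.

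**Censoring.** Under-detection creates the missed event; the censoring rule keeps the untested subject in the risk set. Illustration with recurrence only: true 5-year value 75%, and 20% of subjects never assessed, independently of risk. The current rule gives 1 − 0.25 × 0.80 = 80%. Censoring at the last documented assessment gives about 75%.

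**Goals.** The PFS goals are 15/51.6 = 0.29, 15/50 = 0.30 and 10/35 = 0.29 of the OS goals, consistent with the protocol's basis of roughly one third. The lowest true PFS assumed here, 50%, is already far above all three, so these shifts would not change the comparison.

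**The case against.** The strongest reply is that a disease-state field is clearly planned. The synopsis lists it, and the SAP names its coded categories, so the gap may be no more than a missing table row. Nothing bars sites from using standard-of-care results at the time of the call. Protocol 12.1 keeps reporting, after day 30, AEs that the surgeon attributes to the underlying surgical indication. Deaths are collected throughout, so a missed recurrence followed by death within 5 years still becomes an event.

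Much of this stands, and it rules out several stronger readings that a reader might infer:

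- *No disease state is collected after day 30.* This is true of Table 6 only.
- *Everyone is censored at last contact.* That rule applies only to subjects lost to follow-up; completers are censored at the 5-year visit.
- *Phone reports cannot be verified.* Protocol 10.7 requires data to be traceable to source and does not list disease state among the items for which the CRF may serve as source. The gap is that no particular evidence is named, and a call note could satisfy the rule while documenting only what the subject said.
- *The miss rate applies to every event.* At a true PFS of 50% with 30% missed, that gives 1 − 0.50 × 0.70 = 65%, or +15 points. This exceeds the OS of 64.5%, which is impossible. The simulated figure is +4.5.
- *The estimates are shown to be too high.* The share missed is unknown, so the bias is conditional on incomplete detection. Losses to follow-up were not simulated and could add bias of their own.

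What remains is that nothing requires or records use of medical records, and the AE route works only if the surgeon already knows of the recurrence.

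**Conclusion.** The point holds as a gap in specification with a known direction and an unknown size. Table 6 omits an item that the SAP needs, neither document names the evidence behind it, and event-free time accrues without any disease assessment. Wherever some recurrences stay unknown to the site, 5-year PFS and DFS are biased upward.

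The illustrations run from about 1.4 to 11.4 points with exact yearly visits and from 2.4 to 12.2 points with the visit window. They assume the true PFS values, detection of 90% to 50% of recurrences, complete capture of deaths and no losses.

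A reader might infer that the primary endpoints or trial success are at risk. They are not: Protocol 14.1 ties success to the primary endpoints alone. No power or alpha changes, and the comparison with the 15/15/10% goals is unlikely to change. The value of the correction lies in making the long-term oncologic estimates interpretable.

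**What to change.** 1. **Protocol Table 6.** Add a row for Visits 4-8, *Disease state (from medical record)*, recording the state, its basis and the assessment date from standard-of-care records alongside the call. No additional tests are needed.
2. **SAP 7.9.3.1.** Date PFS and DFS events at the documented assessment where one is available.
3. **SAP 7.9.3.5.** For PFS and DFS, censor event-free subjects at the last documented disease assessment; keep last contact for OS. Code a year without an assessment as *not assessed*, not as disease-free.
4. **Reporting.** Give the number of subjects with a documented assessment each year, and keep the current censoring rule as a sensitivity analysis.

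The cost is one table row, one eCRF page, SAP wording and a short yearly chart review per oncologic subject. Some subjects will be censored earlier and intervals will widen. The new rule is not free of bias: if untested subjects are mainly well, censoring them early is informative and can pull the estimate down. That is why both rules should be shown.
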